5.3 Lifestyle Considerations

Please see Section [6.5](#) for medications that are prohibited during this study.

Subjects must refrain from immersing their head fully under water (eg, swimming, diving) from the time of signed informed consent until after the final study exit visit (Day 21).

5.3.1 Meals and Dietary Restrictions

1. Subjects should abstain from consuming grapefruit, grapefruit juice, cranberry juice, and other cranberry containing products or any products made with Seville oranges (eg, orange marmalade) from 14 days before admission to the study center until after the final study exit visit (Day 21).

5.3.2 Caffeine and Alcohol

1. Subjects will abstain from caffeine or xanthine-containing products for at least 48 hours prior to admission to the study center and for the duration of the stay in the study center.
2. Subjects will abstain from alcohol from Screening until after the final study exit visit (Day 21).

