- g Includes general appearance, overall status of the skin, head, neck, trunk, eyes, heart and lungs (eg, breathing sounds), abdomen, extremities, lymph nodes. Height and weight are recorded only at the Screening visit.
- h Vital signs include blood pressure, respiratory rate, pulse rate, and body temperature.

- i A single 12-lead ECG will be collected for screening purposes. For subjects in Cohort A, a single 12-lead ECG will be collected on Day 1 prior to the first dose and on the study exit visit (Day 21). For subjects in Cohort B, triplicate ECGs will be collected on Day 1: 30 and 60 minutes prior to the first dose, Day 14: 30 minutes prior to the last dose and 5, 20, 35, 50 minutes following the last dose on Day 14. In cases where ECG and PK sampling overlap, ECGs should be collected first, to ensure that PK samples are collected at the scheduled time point.
- j Otoscopy involves ear endoscopy, taking a picture of the tympanic membrane and assessing if there are any abnormal findings.
- k Nasal endoscopy will include a measurement of nasal cavity length (in mm) at the Screening visit only. For all other scheduled assessments, the nasal and epipharynx endoscopy assessment should be done prior to the first dose of the day.
- l Includes hematology, clinical chemistry, coagulation and urinalysis (see [Table 8, Appendix 3](#)).
- m At Screening, a total UPSIT score of ≥ 35 (for females) and a total UPSIT score of ≥ 34 (for males) is required to meet study enrollment criteria.
- n To be collected at the Day 21 study exit visit only if abnormal at the Day 14 visit. Abnormal is defined as UPSIT score < 35 (for females) and < 34 (for males) (see [Section 8.2.8](#)).
- o Audiology pure tone hearing test if abnormal in either ear at Day 14 visit. Abnormal defined as > 20 dB worsening from baseline at Day 14 visit ([Rosenfeld et al, 2004](#)). Typanometry is performed along with the Audiology pure tone hearing test so if the subject requires a hearing test at this visit, tympanometry will also be performed.
- p Audiology pure tone hearing test and tympanometry not required if subjects drops out before Day 14, but if they drop out after Day 14 and had an abnormal test result at Day 14 visit, then every effort should be made to have the patient complete these assessments at the EaT visit.
- q Study subjects need to be trained on study treatment administration on Day -1 or on Day 1, prior to the first dose.

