4.0 STUDY DESIGN

4.1 Overall Design

This is a randomized, double-blind, placebo-controlled, parallel-group, dose-escalation study in healthy volunteers to evaluate the safety and tolerability of OP0201 administered intranasally 3 times a day (TID) using a MDI compared to a matching placebo (HFA-134a minus active ingredients) administered intranasally TID using a MDI for 14 consecutive days (see [Figure 1](#) for the study schematic). The plan is to enroll up to 30 subjects at 1 study center in the US. Two dose cohorts are planned (Cohort A and Cohort B; N=15 per cohort, see Cohort Dosing below, [Table 5](#)). Within each cohort, subjects will be randomized in a 4:1 ratio to receive either OP0201 or placebo. After all subjects in Cohort A have completed the Day 14 visit, a Safety Review Committee (SRC) will review all the blinded safety data to determine whether the doses administered are safe and well tolerated. The SRC will make a recommendation to escalate to the next cohort (Cohort B) or not.

Table 5 Dose Cohorts and Dose Regimen

Cohort	Dose Regimen	Cohort Dose Allocation		Total Subjects in Each Cohort	Total Subjects Per Dose Group
		Per Day Total Dose (mg)	Cumulative Total Dose (mg)		
A	2 sprays per nostril TID x 14 days	OP0201 (30 mg) ^a Placebo (0 mg)	OP0201 (420 mg) ^a Placebo (0 mg)	15	N=12 (OP0201) N=3 (Placebo)
B	4 sprays per nostril TID x 14 days	OP0201 (60 mg) ^a Placebo (0 mg)	OP0201 (840 mg) ^a Placebo (0 mg)	15	N=12 (OP0201) N=3 (Placebo)

a 2.5 mg per spray

N = number of subjects; TID = 3 times a day

Potential subjects will be screened for eligibility during a screening period (Days -28 to -1). Eligible healthy volunteers will be admitted to the study center on Day -1 and be randomized on Day -1. Subjects will remain resident at the study center until after all the Day 15 assessments have been completed (see [Table 3](#) for the Schedule of Assessments [SoA]), with a study exit visit at Day 21.

Study treatment will be administered to the subjects by study center staff TID for 14 days while resident at the study center.

The estimated duration of participation in the study for each subject is up to 54 days: Screening (Days -28 to -1), treatment (Day 1), 16-day residency (Day -1 to Day 15 with safety assessments at Days 4, 8, 14 and 15), study exit (Day 21 [+5 days]). No efficacy assessments will be performed for this study.

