8.2.3 Electrocardiograms

- A single 12-lead ECG will be performed at the Screening visit to ensure that a study subject does not have, in the Investigator's clinical judgement, a clinically significant condition or a condition that may pose an unacceptable safety risk for participation in the study.
- For subjects in Cohort A, a single 12-lead ECG will be collected on Day 1 prior to the first dose and on the study exit visit (Day 21).
- For subjects in Cohort B, triplicate 12-lead ECGs will be collected at subsequent visits as outlined in the SoA (see Section 1.3) using an ECG machine that automatically calculates the heart rate and measures PR, QRS, QT, and QTc intervals.
- In cases where ECG and PK sampling overlap, ECGs should be collected first, to ensure that PK samples are collected at the scheduled time point.
- At each time point at which triplicate ECGs are required, 3 individual ECG tracings should be obtained as closely as possible in succession, but no more than 2 minutes apart. The full set of triplicates should be completed in less than 4 minutes.
- ECGs will be assessed by a central ECG reading center. A cardiologist will review screening, pre- and post-treatment ECGs and discuss any abnormal findings with the Investigator, as appropriate.

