7.5. BASELINE

Baseline is defined as the last scheduled non-missing measurement taken prior to dosing and will

Document: Statistical Analysis Plan
Author: [REDACTED]

Version Number:
Version Date:

2.0
03APR2019

correspond to: Screening assessment for clinical laboratory; Day -1 assessment for Vital Signs; Day 1 pre-dose assessment for ECG in Cohort A, and the average of the mean triplicate ECG assessments at Day 1, 60 minutes pre-dose and Day 1, 30 minutes pre-dose for ECG in Cohort B; Screening assessment for Physical Examination; Day -1 assessment for Otoscopy, Tympanometry, and Nasal and Epipharynx Endoscopy ; and Screening assessment for University of Pennsylvania Smell Inventory Test (UPSIT) Olfactory test, and Audiology Pure Tone hearing test. However, if a subject is missing the planned baseline collection then the last non-missing evaluation prior to dosing (scheduled or unscheduled), if available, will become the baseline value.

For PK assessments, baseline serum concentration is defined as the mean of the two predose serum concentrations observed in samples collected on Day 1 prior to the first dose. If one predose sample is missing, the other Day 1 predose concentration will be used for baseline correction.

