17.9. VITAL SIGNS

The following Vital Signs measurements will be reported for this study:

- Sitting Systolic and Diastolic Blood Pressure (mmHg)
- Pulse Rate (bpm)
- Respiratory Rate (breaths/min)
- Temperature (°C)

The following summaries will be provided by treatment for vital signs data:

- Observed and change from baseline for all post-baseline assessments.

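### The caffeine restriction ends at discharge on Day 15, so the Day 21 vital signs and Cohort A's only scheduled post-baseline ECG are compared with a caffeine-restricted baseline

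*Protocol*

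**What the plan says.** Protocol 5.3.2, item 1, requires abstinence from caffeine and xanthines "for at least 48 hours prior to admission to the study center and for the duration of the stay in the study center". Protocol 4.1 fixes the end of that stay: "Subjects will remain resident at the study center until after all the Day 15 assessments have been completed". The last visit is given there as "study exit (Day 21 [+5 days"]).

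Item 2 of the same section runs longer: "Subjects will abstain from alcohol from Screening until after the final study exit visit (Day 21"). The limits on grapefruit and similar products (5.3.1), head immersion (5.3) and other drugs (6.5) also run to the Day 21 visit, and strenuous exercise is restricted for the whole study (5.3.3).

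For Cohort A, Protocol 8.2.3 says that after Screening "a single 12-lead ECG will be collected on Day 1 prior to the first dose and on the study exit visit (Day 21"). For Cohort B, footnote i of the Schedule of Activities places the post-dose ECGs in confinement: "30 minutes prior to the last dose and 5, 20, 35, 50 minutes following the last dose on Day 14". The Schedule marks vital signs at Day 21 for both cohorts.

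SAP 7.5 sets the baselines: "Day -1 assessment for Vital Signs; Day 1 pre-dose assessment for ECG in Cohort A". SAP 17.9 then summarizes vital signs as "Observed and change from baseline for all post-baseline assessments". SAP 17.8 does the same for ECG by study day, and SAP 17.8.1 flags QTcF increases above 30 and above 60 msec.

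**The concern.** The protocol treats caffeine as worth controlling up to and during the treatment period, then stops controlling it before the final measurement. Baseline and exit readings are therefore taken under different rules, and no reason is given for ending this restriction earlier than the others.

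ECG and vital signs are part of the primary endpoint (SAP 3.1). SAP 17 plans no between-group comparison of safety data unless a section says otherwise, so the tables will largely be read as change from baseline within each group. If some subjects resume caffeine and it affects heart rate, blood pressure or intervals, that effect appears as change at Day 21. It cannot be told apart from a late drug effect or from recovery.

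The Cohort A ECG is the most exposed, because no other scheduled visit can corroborate or correct it. The individual QTcF flags are exposed as well. The stopping criteria in Protocol 4.6.3 also use a QTcF increase of more than 60 ms over baseline, and for Cohort A completers the exit ECG is the only scheduled tracing that can show one.

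**Working it through.** The plan has no figure of its own to reproduce, because Protocol 9.2 states that the sample size has no statistical basis. The check sets the restriction window against the measurement schedule.

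**Unrestricted interval.** Discharge is on Day 15 and exit on Day 21 to Day 26. 21 − 15 = 6 days and 26 − 15 = 11 days.

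**Which comparisons cross the boundary** (subjects who complete):

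| Measurement | Baseline (SAP 7.5) | Post-baseline visits under the restriction | Post-baseline visits not under it |
|---|---|---|---|
| Vital signs, both cohorts | Day -1, restricted | Days 4, 8, 14, 15 | Day 21 |
| ECG, Cohort A | Day 1 pre-dose, restricted | none | Day 21 |
| ECG, Cohort B | Day 1 pre-dose, restricted | Day 14 (pre-dose and 5 to 50 minutes post-dose) | unclear |

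The last cell is unclear because the Schedule grid marks a Day 21 ECG without limiting it to a cohort, while footnote i lists none for Cohort B.

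So one of the scheduled vital-sign visits is affected, against the whole of Cohort A's scheduled post-baseline ECG data. Early-termination ECGs are contingent. SAP 7.6 groups early-termination results with the Study Exit summaries, so a subject leaving during confinement could contribute a caffeine-restricted value to that row.

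**What the placebo subjects can resolve.** Allocation is 12 OP0201 to 3 placebo per cohort (Protocol Table 5). With a common SD of change, the standard error of the difference in mean change is SD × √(1/n₁ + 1/n₂).

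- Cohort A ECG, 12 against 3: √(1/12 + 1/3) = √0.4167 = 0.65 SD. With t on 13 df = 2.16, the 95% half-width is 2.16 × 0.6455 ≈ 1.39 SD.
- Day 21 vital signs, one dose group of 12 against the pooled placebo group of 6 (SAP 7.2): √(1/12 + 1/6) = 0.50 SD. With t on 16 df = 2.12, the half-width is about 1.06 SD.

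The documents give no SD, so these stay in SD units.

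**Size of a caffeine effect.** This cannot be computed. The documents give neither how much caffeine subjects take after discharge nor what it does to any endpoint.

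**The case against.** The strongest reply is that randomization already handles this. The primary objective is a comparison with placebo. Placebo subjects are discharged on the same day, resume caffeine under the same rule and return in the same window, and the SAP shows placebo beside each dose group. In expectation the caffeine effect cancels between arms. That stands, and a reader who inferred a biased active-placebo contrast would be wrong. It does not protect within-arm change or an individual subject's QTcF flag, and with 3 Cohort A placebo subjects the realized balance may be poor.

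It also stands that the on-treatment vital signs are untouched. Conclusions about blood pressure and pulse during dosing do not rest on Day 21.

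A reader might infer that the ECG comparison of 30 mg with 60 mg is confounded by caffeine, because Cohort A is measured unrestricted and Cohort B restricted. The documents do not support making that a point. SAP 17.8 summarizes ECG by study day and plans no comparison of Cohort A at Day 21 with Cohort B at Day 14. Anyone who made it would first meet the difference in timing: within 50 minutes of the last dose in Cohort B, and at least 7 days after the last dosing day in Cohort A. A caffeine rule would not remove that difference.

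A reader might also want to attach a size. If one assumed a systolic effect of 2 to 6 mmHg and an SD of change of 8 to 10 mmHg, the standard error of a 12-subject mean would be 8/√12 = 2.31 to 10/√12 = 2.89, and the shift 2/2.89 = 0.7 to 6/2.31 = 2.6 standard errors. None of these inputs is in the documents. The calculation presumes that every subject shows the effect, and it says nothing about ECG. It should not be relied on.

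Finally, differing restriction lengths are not a contradiction, and tying caffeine to residency is a coherent choice. That is fair: the longer alcohol and grapefruit limits do not prove an error.

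**Conclusion.** The mismatch is certain and its effect is unknown. For completers, all of Cohort A's scheduled post-baseline ECG change and the Day 21 vital-sign change in both cohorts compare an unrestricted reading with a restricted baseline. What is weakened is within-arm interpretation at one off-treatment visit and the individual QTcF change flags in Cohort A. The randomized contrast and the on-treatment vital signs are not affected. The point matters only if subjects resume caffeine and it moves these measurements, and the documents speak to neither. It is a low-cost optional improvement and does not threaten the trial's conclusions.

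**What to change.** In Protocol 5.3.2, item 1, add: *and for at least 48 hours before the Day 21 study exit visit*. This matches the existing pre-admission rule. Record self-reported compliance at that visit.

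The cost is one line of text, a reminder at discharge and two days of outpatient abstinence. Compliance can be checked only by self-report, since caffeine is not among the urine screen analytes in Appendix 3, Table 8.

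If the protocol text cannot change, state the limitation in the SAP for the Day 21 ECG and vital-sign summaries, and read the Day 21 ECG alongside the Screening ECG. SAP 17.8 already summarizes the Screening ECG, and it too falls outside the restriction unless screening takes place within 48 hours of admission. This alternative costs nothing in conduct but leaves the mismatch in the baseline comparison.

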5.3.3 Activity

1. All subjects must comply with the contraception requirements as noted in [Appendix 6](#).
2. Subjects should refrain from strenuous exercise for 24 hours before Screening, before admission and for the duration of the study.
3. Subjects will be advised not to donate blood or plasma for at least 3 months after the last dose administration.

5.4 Screen Failures

Screen failures are defined as subjects who consent to participate in the clinical study but are not subsequently randomly assigned to study treatment. A minimal set of screen failure information is required to ensure transparent reporting of screen failure subjects to meet the Consolidated Standards of Reporting Trials publishing requirements and to respond to queries from regulatory authorities. Minimal information includes demography (eg, age, gender, race), reasons for screen failure (eg, note which eligibility criteria was not met), and any SAE.

Individuals who do not meet the criteria for participation in this study (screen failure) may not be rescreened.

6.0 STUDY TREATMENT

Study treatment is defined as any investigational treatment(s), marketed product(s), placebo, or medical device(s) intended to be administered to a subject according to the study protocol.

The study treatment is to be used in accordance with the protocol for healthy volunteers who are under the direct supervision of a qualified Investigator.

6.1 Study Treatment(s) Administered

The following study treatments will be used in this study.

Study Treatment #1: OP0201

OP0201 is an intranasal aerosol, a dosage form recognized by the US Pharmacopeia, that is comprised of 2 active ingredients, DPPC and CP, in approximately 20:1 (w/w) ratio, suspended in an inactive ingredient, the synthetic chlorofluorocarbon-free propellant HFA 134a. All OP0201 ingredients are synthetic; none of these ingredients contain any animal or human derivatives. OP0201 is supplied in mechanical packing parts that includes a pressurized canister with a securely attached metering valve where the drug product is contained, an actuator into which the canister is seated and the valve connects with device body, and a tip to deliver the drug to the nostrils.

OP0201 is manufactured using Good Manufacturing Processes (GMP) with development phase appropriate compliance with global Health Authority guidelines (eg, [US FDA Guidance for Industry: Nasal Spray and Inhalation Solution, Suspension and Spray Drug Products, July 2002](#)) by [REDACTED]. The OP0201 canisters are filled to deliver 100 actuations (sprays) per canister. Each MDI spray of OP0201 delivers 0.1 mL of HFA-134a containing a total of 2.5 mg of the active pharmaceutical ingredients as dry powder suspended in the HFA-134a.

See the IB for further details regarding OP0201.

Study Treatment #2: Placebo

The placebo is comprised of the same synthetic chlorofluorocarbon-free propellant, HFA-134a, an inactive ingredient as used in the study treatment #1 described above. The placebo is manufactured using GMP with development phase appropriate compliance with global Health Authority guidelines (eg, [US FDA Guidance for Industry: Nasal Spray and Inhalation Solution, Suspension and Spray Drug Products, July 2002](#)) by [REDACTED].

The placebo canisters are filled to deliver 100 actuations (sprays) per canister. Each 0.1 mL MDI spray of placebo delivers 0.1 mL of HFA-134a.

For each dose, the subject will have administered to them by the study center staff, 2 (Cohort A) or 4 (Cohort B) consecutive sprays first to the left nostril and then to the right nostril for a total of 4 (Cohort A) or 8 (Cohort B) sprays (see Study Manual for Study Treatment Instructions for Use). The dose will be repeated 3 times a day for a total of 14 days (42 doses).

The study treatment will be administered every 7 hours: a morning dose at 9:00 am, an afternoon dose at 16:00 pm and an evening dose at 23:00 pm. The Investigator or qualified designee will record each dose by noting the time and number of total sprays administered successfully in a dosing log.

6.2 Preparation/Handling/Storage/Accountability

1. The Investigator or designee must confirm appropriate temperature conditions have been maintained during transit for all study treatment received and any discrepancies are reported and resolved before use of the study treatment.
2. Only subjects enrolled in the study may receive study treatment and only authorized study center staff may supply or administer study treatment. All study treatments must be stored in a secure, environmentally controlled, and monitored (manual or automated) area in accordance with the labeled storage conditions with access limited to the Investigator and authorized study center staff.
3. The Investigator, institution, or the head of the medical institution (where applicable) is responsible for study treatment accountability, reconciliation, and record maintenance (ie, receipt, reconciliation, and final disposition records).

The Investigator, a member of the study center staff, or a pharmacist must maintain an adequate record of the receipt and distribution of all study medication using the Drug Accountability Form. These forms must be available for inspection at any time.

6.3 Measures to Minimize Bias: Randomization and Blinding

6.3.1 Study Treatment Kit

Each study treatment kit will be labeled with a kit number and contain a predetermined number of units. For this study, a unit is defined as 1 canister of study treatment. Each kit will include the necessary amounts of units of study treatment; according to the study treatment cohort and dose level. Further details will be provided in the Laboratory Manual.

On Day 1 subjects will be assigned a unique number (randomization number) in ascending numerical order. The randomization number encodes the subject's assignment to 1 of the 2 study treatments of the study, according to the randomization schedule generated prior to the study by the Statistics Department at the Sponsor or designee. Each subject will be assigned blinded study treatment, labeled with his/her unique randomization number, that will be used throughout the study.

Within each dose cohort, subjects will be randomly assigned in a 4:1 ratio to receive OP0201 or placebo. The randomization scheme will be prepared by the Sponsor's designee.

6.3.2 Blinding

Study treatment will be provided in identically appearing canisters and kits to maintain masking of the study.

6.3.3 Procedures for Unblinding Study Treatment

A sealed envelope that contains the study treatment assignment for each subject will be provided to the Investigator. The sealed envelope will be retained by the Investigator (or representative) in a secured area. In case of an emergency, the Investigator has the sole responsibility for determining if unblinding of a subject's treatment assignment is warranted. Subject safety must always be the first consideration in making such a determination. If the Investigator decides that unblinding is warranted, the Investigator should make every effort to contact the Sponsor and Medical Monitor prior to unblinding a subject's treatment assignment unless this could delay emergency treatment of the subject. If a subject's treatment assignment is unblinded, the Sponsor and Medical Monitor must be notified within 24 hours after breaking the blind. Once the study is complete, all envelopes (sealed and opened) must be inventoried and returned to the Sponsor.

